Official Title:

Evaluation of the Effects of Subspinal Le Fort and Conventional Le Fort I Osteotomy on Nasolabial Soft Tissues

NCTNumber:

NCTXXXXXXXXX

Not yet assigned

Document Date:

January 2021

DocumentType:

Study Protocol

Statistical Analysis Plan

Study Design

This controlled clinical study was designed as a single-center, prospective, randomized, and double-blind trial.

All volunteers will be informed about the medications to be used in the study, possible side effects, the surgical procedure, and potential complications, and their informed consent will be obtained.

The present study will investigate the potential differences in nasal soft tissue changes associated with the modification of subspinal osteotomy compared to the conventional technique used in Le Fort I osteotomy, without making any changes to the routine orthognathic surgery and postoperative follow-up protocols conducted in our clinic.

Selection Criteria

Volunteers will be selected from patients presenting to our clinic with functional, aesthetic, and phonation complaints due to skeletal orthodontic anomalies and who are scheduled to undergo Le Fort I and/or Bilateral Sagittal Split Osteotomy under general anesthesia.

Participants will be divided into two groups according to the osteotomy technique. From both groups, a total of 30 patients aged between 18–40years, without acute infection, with ASA I–II classification, no systemic disease, no history of hypersensitivity to any medication, normal hemoglobin levels (female: 12–14 g/dL; male: 14–16 g/dL), INR <1.5, and no history of NSAID use within one week prior to surgery will be included.

Patients with ASA III or higher physical status, hepatic or renal dysfunction, neuropathic disease, long-term NSAID or opioid use, a history of drug allergy, preoperative pain, swelling or inflammation in the head and neck region, and those who are pregnant or breastfeeding will be excluded from the study.

A total of 30 patients included in the study will be randomly divided into two groups (n=15 each):

- Group I: Subspinal Le Fort I osteotomy group (n=25)
- Group II Conventional Le Fort I osteotomy group (n=25)

Before the operation, all patients will be informed about the type of osteotomy to be performed and the use of 3D photography for postoperative edema assessment.

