Patients will complete the ROE (Rhinoplasty Outcome Evaluation) scale preoperatively and at 6 months postoperatively to provide a subjective evaluation of their aesthetic and functional outcomes.

To ensure consistency between preoperative and postoperative imaging, craniocervical angle measurements will be performed, and only images without statistically significant differences will be included. Changes in maxillary position (anterior and/or superior movement) and their effects on nasal tissues will be analyzed.

Preoperative and postoperative measurements will be performed twice by a single researcher at two-week intervals using dedicated software, and the mean values will be recorded.

Maxillary movements at Point A (Pt A), posterior nasal spine (PNS), incisor superius (Is), and anterior nasal spine (ANS) will be evaluated in the X, Y, and Z coordinate system (X-axis: transverse, Y-axis: sagittal, Z-axis: vertical) following conventional or subspinal Le Fort I osteotomy.

The following anatomical landmarks will be identified: alar (Al), alar curvature (Ac), soft tissue glabella (Gs), soft tissue nasion (Ns), pronasale (Prn), columella (Cm), subnasale superior (Sns), subnasale (Sn), and labrale superior (Ls).

The following measurements will be performed:

1. Nasal width
 2. upper lip length
 3. Alar base width
 4. columellalobular angle
 5. Nasal tip angle
 6. Nasolabial angle
 7. Nostril width
-
-

Postoperative Edema Assessment

Postoperative edema will be evaluated using the 3dMD three-dimensional imaging system.

3D images will be obtained at the following time points:

- Preoperative day 1 (T0)
- Postoperative day 1 (T1)
- Postoperative day 3 (T2)
- Postoperative day 7 (T3)
- Postoperative month 1 (T4)
- Postoperative month 3 (T5)
- Postoperative month 6 (T6)

Images will be captured with patients in maximum intercuspation, with relaxed lips and open eyes. All images will be obtained by the same clinician.

Rhinoplasty outcome evaluation (roe scale)

The Rhinoplasty Outcome Evaluation is a patient-reported outcome measure designed to assess satisfaction with nasal appearance and function following rhinoplasty.

Measurement:

It consists of 6 questions, each scored from 0 (most negative) to 4 (most positive); the total score is summed, divided by the maximum possible score (24), and multiplied by 100 to yield

a percentage score ranging from 0 to 100, where higher scores indicate greater patient satisfaction.

Processing of 3D Images

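### The trial is labelled double-blind, but on the plain reading patients are told their osteotomy technique before surgery, so the 6-month ROE is an unblinded subjective outcome

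*Combined protocol and SAP*

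**What the plan says.** The Study Design section describes a "single-center, prospective, randomized, and double-blind trial". Neither that section nor any later one says which parties are blinded or how.

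Under Selection Criteria, the arms are set by the operation itself: "Participants will be divided into two groups according to the osteotomy technique". Group I receives subspinal Le Fort I osteotomy and Group II conventional Le Fort I osteotomy. Directly after that list comes the sentence: "Before the operation, all patients will be informed about the type of osteotomy to be performed". It goes on to mention the 3D photography.

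The outcome paragraphs that follow state: "Patients will complete the ROE (Rhinoplasty Outcome Evaluation) scale preoperatively and at 6 months postoperatively". The section on the ROE scale adds: "The Rhinoplasty Outcome Evaluation is a patient-reported outcome measure designed to assess satisfaction with nasal appearance and function following rhinoplasty".

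The same outcome paragraphs assign the preoperative and postoperative measurements to one researcher, who makes them twice, two weeks apart, and records the mean. Nothing is said about whether that researcher knows the group.

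**The concern.** A double-blind label tells readers that knowledge of the arm was kept from those who could influence the results, and most will take that to include the patients. Here the patient is the assessor of ROE, the only patient-reported outcome described. If the patient knows the technique, beliefs about it can enter the score. Randomization does not remove a difference that arises this way, and a larger sample does not dilute it. Once patients have been told, the knowledge cannot be withdrawn or adjusted for in the analysis. A report that carried the label forward would misdescribe the evidence on patient satisfaction.

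The measurements raise a related but distinct question. Identifying landmarks involves judgment. Averaging two readings reduces random error but would not remove a systematic tendency in a reader who knew the group. The plan should say whether that reader is masked.

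**Working it through.** The plan gives no figure on blinding to reproduce, so the check is a comparison of passages.

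1. **The label.** Study Design says double-blind and names no blinded party.
2. **What separates the arms.** Selection Criteria defines the groups by osteotomy technique, and Study Design says routine surgery and follow-up are otherwise unchanged. Knowing the technique is therefore the same as knowing the arm.
3. **What patients are told.** The disclosure sentence covers all patients, refers to the osteotomy that is going to be done, and directly follows the list of the two groups. General information about the operation is already covered in Study Design: "All volunteers will be informed about the medications to be used in the study, possible side effects, the surgical procedure, and potential complications". The later sentence would add little if it meant only that. The plain reading is that it conveys the allocated technique.
4. **When ROE is completed.** There are two occasions, preoperative and 6 months. The order of the preoperative ROE and the disclosure is not given, so the baseline score may or may not precede it. The 6-month score necessarily follows it.
5. **Whether anything restores patient blinding.** No section provides for withholding the allocation from patients.
6. **Who else might be blinded.** The surgeon must know the technique. The plan also involves a clinician who captures all images, a researcher who measures, whoever does the superimposition and volumetric analysis, and whoever runs the statistics. It does not say whether these are different people, and describes none of them as masked.
7. **Size of the effect on ROE.** The scale has 6 items scored 0 to 4, so the maximum is 6 × 4 = 24, and one category on one item is 1/24 × 100 = 4.17 points. That is the resolution of the scale, not an estimate of bias. An estimate would need the shift caused by knowing the arm, and the documents contain nothing from which to derive it.

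Steps 1 to 5 establish the contradiction for patients. Step 6 shows a separate omission that does not follow from what patients are told.

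**The case against.** The strongest reply is that the sentence does not refer to the allocated arm. Patients are enrolled for Le Fort I and/or Bilateral Sagittal Split Osteotomy, so the type of osteotomy could mean which jaw operation is planned, or a description of the techniques under study. The mention of photography in the same sentence gives it the flavour of a general briefing. This reading is available but weaker, given where the sentence stands and that a general briefing is already provided for. If it is what the sponsor meant, the text still has to say so.

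A second reply is that double-blind may have meant assessor and analyst. The documents neither say this nor exclude it. A reader might infer that the measuring researcher is the only other person who could be blind, so that no form of double-blinding is possible. That does not follow, since several other roles exist. What stands is that the claim fails for patients and is unspecified for everyone else.

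A third reply concerns weight. The stated aim is nasal soft tissue change assessed by imaging, and ROE has no designated primary role. A patient's knowledge has little obvious route into a measure such as nasal width. This is fair: the point bears on ROE and on the design label, and the imaging comparison is not undermined by what patients are told.

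**Conclusion.** The concern holds for patients. On the plain reading they know their arm, the 6-month ROE is an unblinded subjective outcome, and the double-blind description is wrong as written. This rests on taking the disclosure sentence to mean the allocated technique; under the softer reading, the defect is an ambiguity that still needs correcting. The plan's silence on masking of the measuring researcher is a second, separate gap.

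Three stronger conclusions may tempt a reader and are not supported:

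- **That the measuring researcher knows the group and the soft-tissue measurements are biased.** The documents are silent on this; they do not say the researcher is aware of the allocation, and they support no direction of bias.
- **That ROE will favour the subspinal arm because patients expect it to be better for the nose.** The protocol calls it only a modification of the conventional technique, and does not say patients will be told it is superior.
- **That the bias can be put at some number of ROE points.** Any such figure would multiply the 4.17-point step by an arbitrary number of shifted items. Neither size nor direction can be estimated from the documents.

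**What to change.** Replace the disclosure sentence with wording such as: *Both osteotomy techniques will be explained to every patient before surgery; the technique allocated will be withheld from the patient until the 6-month ROE has been completed.* Match the consent text to it, and state in Study Design which parties are blinded.

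For the measurements, export images under a random code that carries no group information, and have the existing researcher, masked to allocation, measure them in random order.

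If disclosure to patients cannot be avoided, remove the double-blind label. Use assessor-blind only if the image coding is adopted, since otherwise that label would be unsupported too. Report ROE explicitly as an unblinded outcome.

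The cost is modest but goes beyond editing one sentence. Patients wait six months to learn their technique, the treating team must avoid revealing it at follow-up visits, the consent change needs ethics review, and the image files have to be coded. No change to the surgery or the visit schedule is involved.

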Anatomical landmarks will be identified on 3D images to superimpose preoperative and postoperative scans. Six reference points will be used: bilateral medial and lateral canthi (four points), nasion, and trichion.

Images will be superimposed, and volumetric analyses will be performed using 3dMD Vultus Software (3dMD, Atlanta, GA, USA).

Statistical Analysis

All statistical analyses will be performed using SPSS 22.0 (SPSS Inc., Chicago, IL, USA).

Descriptive statistics (mean, standard deviation, minimum, maximum) will be used to define continuous variables. Normality of data distribution will be assessed using the Shapiro–Wilk test.

Comparisons between groups will be performed using one-way ANOVA and Tukey post hoc analysis.

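### The only planned test has no baseline covariate and no movement term: the technique comparison stays valid but may lose precision, and the movement aim has no analysis

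*Combined protocol and SAP*

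**What the plan says.** The combined protocol and SAP sets two questions. *Study Design* asks about "potential differences in nasal soft tissue changes associated with the modification of subspinal osteotomy compared to the conventional technique". The measurement paragraphs ahead of *Postoperative Edema Assessment* add a second: "Changes in maxillary position (anterior and/or superior movement) and their effects on nasal tissues will be analyzed".

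The same paragraphs show what is collected:

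- Soft-tissue measurements: "Preoperative and postoperative measurements will be performed twice by a single researcher at two-week intervals using dedicated software", with the mean of the two readings kept.
- Patient-reported outcome: "Patients will complete the ROE (Rhinoplasty Outcome Evaluation) scale preoperatively and at 6 months postoperatively".
- Movement: "Maxillary movements at Point A (Pt A), posterior nasal spine (PNS), incisor superius (Is), and anterior nasal spine (ANS) will be evaluated" on three axes, after the osteotomy has been done.

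*Statistical Analysis* provides descriptive statistics, a Shapiro–Wilk check and one method of inference: "Comparisons between groups will be performed using one-way ANOVA and Tukey post hoc analysis". It names no covariate, regression or correlation. It does not say whether the response is the postoperative value or the change from baseline, or which postoperative time point is compared.

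**The concern.** There are two gaps.

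First, the movement aim has no analysis. A one-way ANOVA by technique estimates one mean per group. It has no slope, so it cannot say how nasal change varies with the amount or direction of maxillary movement. If the plan is silent, the choice among four landmarks and three axes will be made after the data are seen.

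Second, the preoperative values have no stated role in the technique comparison. In a trial this small, a covariate that predicts the outcome can narrow the confidence interval noticeably, and here it has already been measured. At stake is power for the main question, not the validity of the test.

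**Working it through.** **Inputs from the document.** Two groups; 15 per arm in one statement and 25 per arm in the group list (*Selection Criteria*). No alpha, SD, effect size, correlation or power is given, so there is no calculation of the plan's own to reproduce.

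**Assumptions.** Equal SDs before and after surgery; pre/post correlation r of 0.5, 0.7 or 0.9; for power, two-sided 5% and a difference of 0.8 SD of the postoperative value.

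**Step 1: what the stated test is.** With two groups, one-way ANOVA is the two-sample t-test (a numerical check gave the same p-value, 0.0468, both ways). Tukey comparisons add nothing when there is only one pair.

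**Step 2: variance of the group difference, relative to a postoperative-only ANOVA.**

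- Postoperative value only: 1.
- Change score: 2(1 − r).
- ANCOVA: (1 − r²) × [1 + 1/(2n − 4)], where the last factor is the small-sample price of estimating the slope. It is 1 + 1/26 = 1.038 at n = 15 and 1 + 1/46 = 1.022 at n = 25.

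At n = 15:

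| r | Change score | ANCOVA | ANCOVA ÷ postoperative-only | ANCOVA ÷ change score |
|---|---|---|---|---|
| 0.5 | 1.00 | 0.75 × 1.038 = 0.78 | 78% | 78% |
| 0.7 | 0.60 | 0.51 × 1.038 = 0.53 | 53% | 88% |
| 0.9 | 0.20 | 0.19 × 1.038 = 0.197 | 20% | 99% |

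At n = 25 the last two columns become 77%, 52%, 19% and 77%, 87%, 97%.

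**Step 3: break-even.** ANCOVA equals the change score when (1 + r)/2 × 1.038 = 1, so r = 2/1.038 − 1, or about 0.93 at n = 15 (0.96 at n = 25). Against a postoperative-only test at n = 15, ANCOVA gains once r exceeds about 0.19; at r = 0 it costs about 4% in variance.

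**Step 4: power at r = 0.7 (noncentral t).**

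| Per arm | Postoperative-only | Change score | ANCOVA |
|---|---|---|---|
| 15 | 56% | 78% | 83% |
| 25 | 79% | 95% | 97% |

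**Step 5: movement in the technique model.** This was simulated at 15 per arm with 10,000 runs: outcome = 0.5 × movement − 0.3 × technique + error (SD 0.8), with movement SD 1.

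- Technique does not alter movement: the estimate is −0.30 with or without adjustment, and its SD falls from 0.34 to 0.29.
- Technique shifts movement by −1 SD: the total effect is −0.3 + 0.5 × (−1) = −0.80. The unadjusted estimate recovers it. The adjusted estimate is −0.30, with almost no precision gain (SD 0.34 against 0.35).

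**Step 6: degrees of freedom at 15 per arm.** ANOVA leaves 28 and ANCOVA on baseline 27. A regression on two movement terms plus group leaves 30 − 4 = 26. Four landmarks on three axes give 12 movement values; baseline plus all 12 would leave 15.

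**The case against.** The best defence is that the technique question is about change, that measurements are taken before and after surgery, and that the natural reading is therefore an ANOVA on change scores. That analysis uses the baseline. This stands. A reader might infer that the plan ignores baseline values, but the document does not establish it; the response is simply not named. On the change-score reading the gain from ANCOVA is moderate at r = 0.7 and about 1% at r = 0.9.

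A reader might also infer that unbalanced movement undermines the technique comparison. It does not. Allocation is random, so chance imbalance is already covered by the test's error rate and confidence interval. If the SD of movement were 2.5 mm (assumed), the arms could differ by chance by up to 1.96 × 2.5 × √(2/15) = 1.8 mm in 95% of trials, or 1.4 mm at 25 per arm. That is a matter of precision, not of bias.

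A third inference is that movement should go into the same model as technique. The document does not support that either. Movement is assessed after the operation, nothing shows that technique leaves it unchanged at any landmark, and planned movement is not mentioned. Step 5 shows how adjustment could remove part of the technique effect.

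Finally, adjustment is not free. A model with baseline and two movement terms carries a factor of 27/24 = 1.125 at 15 per arm. If movement explained nothing further, its variance against change scores would be 0.84, 0.96 and 1.07 at r = 0.5, 0.7 and 0.9. This argues for a single baseline covariate in the main model.

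None of this supplies an analysis for the movement aim.

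**Conclusion.** The point holds in two parts of different strength. That the movement aim has no matching analysis follows from the text alone and needs no assumption. That the technique comparison does not make full use of the preoperative values is also clear from the text, since no covariate is named, but the resulting loss is conditional. At 15 per arm it is large if postoperative values are compared and the pre/post correlation is high. If change scores are compared, it runs from 22% of variance at r = 0.5 to none above about 0.93. These figures rest on assumed correlations and equal SDs, and change little at 25 per arm. The randomised comparison is valid as planned; the case for change is better precision and a complete plan.

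**What to change.** **(a) Technique comparison.** Replace the one-way ANOVA and Tukey test with ANCOVA for each soft-tissue measurement: 6-month value = group + preoperative value. Use the same form for ROE. Report the adjusted group difference with its 95% CI. Six months is both the last 3D image and the postoperative ROE time point. With the preoperative value in the model, the group difference is the same whether the response is the 6-month value or the change, so this also settles the undefined response.

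**(b) Movement aim.** Prespecify a separate regression: nasal change = sagittal (Y) movement + vertical (Z) movement + group, at one named landmark such as Is. Report the slopes with 95% CIs, and label them as associations because movement is measured after randomisation.

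**(c) Keep the two apart.** Do not put achieved movement in the main technique model. Planned movement may be added only if it is recorded before allocation.

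**Cost.** SAP wording, one degree of freedom in the main model (28 to 27 at 15 per arm, 48 to 47 at 25) and a small amount of extra analysis. Both models use data the plan already collects.

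### No primary outcome, no stated analysis visit for the seven soft-tissue measurements, and no control of error across outcomes: the false-positive risk is substantially inflated

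*Combined protocol and SAP*

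**What the plan says.** All references are to the combined protocol and SAP.

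- **Aim (Study Design).** It is general: "The present study will investigate the potential differences in nasal soft tissue changes associated with the modification of subspinal osteotomy compared to the conventional technique". No variable is singled out.
- **Measurement list (before Postoperative Edema Assessment).** "The following measurements will be performed" introduces seven items: nasal width, upper lip length, alar base width, columellalobular angle, nasal tip angle, nasolabial angle and nostril width. They are not ranked. On timing the text says only "Preoperative and postoperative measurements will be performed twice by a single researcher at two-week intervals using dedicated software, and the mean values will be recorded". The two weeks there separate repeat readings; they do not define a follow-up visit.
- **ROE.** This outcome does have a visit: "Patients will complete the ROE (Rhinoplasty Outcome Evaluation) scale preoperatively and at 6 months postoperatively".
- **Oedema (Postoperative Edema Assessment; Processing of 3D Images).** "3D images will be obtained at the following time points" is followed by T0 and six postoperative visits: days 1, 3 and 7, and months 1, 3 and 6. Then "Images will be superimposed, and volumetric analyses will be performed using 3dMD Vultus Software", with no visit or contrast named as the main one.
- **Maxillary movement.** Four bony points "will be evaluated in the X, Y, and Z coordinate system", giving 4 × 3 = 12 further variables.
- **Statistical Analysis.** The only comparison rule is "Comparisons between groups will be performed using one-way ANOVA and Tukey post hoc analysis". There is no significance level, no list of the variables compared, and no adjustment across outcomes or visits.

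**The concern.** With no ranking, the plan does not say which result answers the trial's question. Someone following it could report a difference between techniques on whichever measurement reached significance, and nothing written would make that a departure from plan. Naming Tukey may suggest that multiplicity has been handled, but Tukey adjusts for pairs of groups within one outcome. Here there is one pair of groups and many outcomes.

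The missing visit is a second degree of freedom. If the seven measurements are read from the T0 to T6 images, the choice of visit is open as well. Readings at days 1, 3 or 7 could then record swelling, which the trial itself sets out to track, as nasal change.

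**Working it through.** The plan states no error rate, so there is no figure of its own to reproduce.

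**Inputs**
- Seven measurements, one ROE score and six postoperative oedema volumes (document).
- Two groups. Selection Criteria gives both n=15 and n=25 per group, so both were run.
- Two-sided 5% per test: *assumed*, because no level is stated.
- Each variable compared between groups: *assumed*. Statistical Analysis lists no variables and excludes none.
- Correlation between outcomes: not given, so a range is shown.

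**Step 1. Does Tukey protect?** For two groups the Tukey critical value divided by √2 is 2.048 at 28 degrees of freedom (15 per arm). The two-sided 5% t value is also 2.048. The procedure is the ordinary t test and gives no protection.

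**Step 2. Independent tests.** P(at least one false positive) = 1 − 0.95^k.
- k = 7 (measurements at one visit): 1 − 0.95^7 = 30.2%
- k = 8 (plus ROE): 1 − 0.95^8 = 33.7%
- k = 14 (plus six oedema volumes): 1 − 0.95^14 = 51.2%

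**Step 3. Correlated tests.** Several measurements describe the same small region, so independence is an upper case. Two-sample t tests were simulated under no true difference with a common correlation ρ, using 10,000 trials per cell (Monte Carlo standard error at most √(0.25/10,000) = 0.5 points).

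| Tests | n per arm | ρ=0.3 | ρ=0.5 | ρ=0.7 | ρ=0.9 |
|---|---|---|---|---|---|
| 7 | 15 | 28.0% | 23.4% | 18.5% | 11.3% |
| 7 | 25 | 27.6% | 23.3% | 17.1% | 11.5% |
| 8 | 15 | 30.2% | 25.6% | 19.1% | 12.0% |
| 8 | 25 | 30.1% | 25.6% | 19.0% | 12.1% |
| 14 | 15 | 43.9% | 35.4% | 26.1% | 14.4% |
| 14 | 25 | 44.6% | 36.0% | 25.4% | 13.9% |

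Repeating the ρ=0.5 and ρ=0.7 columns with 200,000 trials per cell gave 18 to 23% for seven tests, 19 to 26% for eight and 25 to 36% for fourteen. The 17.1% cell became 18.0%, so its low value was simulation noise. Group size makes almost no difference.

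**Step 4. Cost of adjusting.** The standardised difference detectable with 80% power (normal approximation) is (z₁₋α/₂ + 0.842) × √(2/n).
- n = 15, α = 0.05: (1.960 + 0.842) × 0.365 = 1.02 SD
- n = 15, α = 0.05/7: (2.690 + 0.842) × 0.365 = 1.29 SD
- n = 25: 0.79 SD and 1.00 SD respectively

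**The case against.** The strongest reply is that the aim is exploratory in tone, the plan writes no confirmatory claim or decision rule, and it never says that every variable will be tested. That is fair, and it is why the rates above rest on labelled assumptions. It does not supply a primary outcome or a visit, and the one comparison sentence excludes nothing.

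A reader might infer three stronger things that the documents do not support.

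- **That a chance finding is likely.** For seven or eight tests the risk stays at about 34% or less. It passes one half only for 14 independent tests, and it falls to about 14 to 45% once those are correlated at 0.9 to 0.3.
- **That all seven measurements will be tested at all six visits.** That would be 7 × 6 + 1 + 6 = 49 tests, and 1 − 0.95^49 = 92% if independent. But the T0 to T6 schedule stands under the oedema heading, and the measurements are described before it, next to bony landmarks. They could come from one preoperative and one postoperative image set. The visit-selection and swelling points are therefore conditional.
- **That the trial could not support a null conclusion either.** Multiple testing inflates false positives. Whether a null result would be informative is a question of precision and sample size, which this point does not address.

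**Conclusion.** The concern holds in a limited form. Three gaps are plain on the text: no primary outcome, no stated analysis visit for the seven measurements, and no error control across outcomes or visits. ROE is not part of the visit gap.

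The resulting risk of at least one false positive is several times the nominal 5% in most of the cases examined, and more than double it even at correlation 0.9. The size depends on the assumed 5% level, on which variables are in fact compared, and on their correlation. The conflict between 15 and 25 per group needs reconciling in its own right but does not alter this conclusion. The 12 maxillary coordinates are outside these counts and would enlarge the family if they too were tested between groups.

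This should be corrected. It is more than missing detail, because the rule as written lets the conclusion rest on any one of many unranked tests.

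**What to change.** Amend the SAP before outcome data are seen by group:

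1. State which images and which postoperative visit supply the seven measurements.
2. Name one primary outcome at one visit, tested at two-sided 5%, and base the trial's conclusion on it. The choice belongs to the investigators; change in alar base width from T0 to T6 is one example. T6 is the last imaging visit and coincides with the postoperative ROE.
3. Make the other six measurements at T6 and ROE at 6 months secondary (6 + 1 = 7 tests), with Holm adjustment.
4. Report oedema volumes, and any soft-tissue measurements from earlier visits, as exploratory, with estimates and 95% confidence intervals only.
5. State that the 12 maxillary coordinates are descriptive or explanatory variables, not outcomes tested for efficacy.

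No extra patients, visits or measurements are needed. The false-positive risk on the primary outcome becomes 5%. The cost falls on the secondary outcomes: they lose stand-alone confirmatory status and some power. At 15 per arm, the first Holm step (0.05/7) needs about 1.29 SD for 80% power, against 1.02 SD unadjusted.

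### One-way ANOVA with Tukey, the only inferential method stated, does not fit two arms measured repeatedly from T0 to T6

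*Combined protocol and SAP*

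**What the plan says.** - **Arms.** Under Selection Criteria: "Participants will be divided into two groups according to the osteotomy technique". There are no others.
- **Repeated imaging.** Under Postoperative Edema Assessment: "3D images will be obtained at the following time points". The list runs from "Preoperative day 1 (T0" to "Postoperative month 6 (T6": seven visits per patient, six of them after surgery.
- **Other outcomes.** Seven soft-tissue measurements are taken before and after surgery, with no dated postoperative visit. ROE is completed before surgery and at 6 months.
- **Aim.** Study Design frames the question as a difference between techniques in nasal soft-tissue change.
- **Method.** Under Statistical Analysis, after descriptive statistics and a Shapiro–Wilk check: "Comparisons between groups will be performed using one-way ANOVA and Tukey post hoc analysis". No paired test, repeated-measures ANOVA, mixed model, change score, baseline adjustment, primary time point or multiplicity rule is named. The section does not say how the visits enter the analysis.

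**The concern.** Tukey's procedure exists to compare three or more independent groups. This trial has two arms, so either Tukey is idle or the groups are something other than the arms. The only evident factors with more levels are visit (seven) and arm by visit (fourteen). Those levels hold the same patients measured again, while one-way ANOVA and Tukey assume independent observations.

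On the first reading, the longitudinal oedema data and the preoperative values have no stated analysis. On the second, the standard errors would be wrong, in a direction that depends on which factor is tested. The sentence permits analyses with very different error rates, so it does not fix the result in advance. It is also the whole inferential plan and governs every outcome.

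**Working it through.** **Inputs from the document.** Two arms; visits T0 to T6; 15 per arm. The arm list under Selection Criteria also gives 25 per arm ("Group I: Subspinal Le Fort I osteotomy group (n=25"), so both sizes were run. The plan states no power, SD, alpha or correlation, so it has no figure of its own to reproduce.

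**Assumptions.** Two-sided alpha 0.05; normal data with SD 1; equal within-patient correlation ρ between all visits, shown over a range. Simulations used 20,000 trials per setting, with no true effect unless a shift is stated.

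**1. Two arms at one visit.**
- Pairs: C(2,2) = 1, and F = t².
- At 15 per arm the critical value is 2.048 for both Tukey and the t-test (28 df). Tukey changes nothing.
- Simulated type I error of the single-visit arm test stays at its level: 0.047 to 0.053.

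**2. That test repeated at six postoperative visits.** Chance of at least one false positive:
- If independent: 1 − 0.95⁶ = 0.265.
- Simulated at 15 per arm: 0.241, 0.207 and 0.165 at ρ = 0.3, 0.5 and 0.7.
- At 25 per arm: 0.243, 0.209 and 0.166.

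**3. Conditional: six visits pooled, one-way ANOVA on arm.** Each arm mean has its variance understated by about 1 + 5ρ. The approximate true type I error is 2[1 − Φ(1.96/√(1 + 5ρ))].

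| ρ | 1 + 5ρ | Approximation | Simulated, 15 per arm | Simulated, 25 per arm |
|---|---|---|---|---|
| 0.3 | 2.5 | 0.215 | 0.216 | 0.217 |
| 0.5 | 3.5 | 0.295 | 0.300 | 0.301 |
| 0.7 | 4.5 | 0.356 | 0.366 | 0.366 |

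**4. Conditional: visits as the factor levels.** Number of pairs: C(7,2) = 21. For N patients, the true variance of a difference between two visit means is 2σ²(1 − ρ)/N; one-way ANOVA uses 2σ²/N.
- SE ratio 1/√(1 − ρ): 1.41 at ρ = 0.5 and 1.83 at ρ = 0.7.
- Simulated type I error of one-way ANOVA on visit: 0.008 or less for ρ = 0.3 and above. A repeated-measures F keeps 0.049 to 0.052.
- Power for a 0.5 SD shift at one visit, ρ = 0.5: 21% one-way against 75% repeated-measures at 15 per arm; 54% against 95% at 25 per arm.

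**5. Conditional: fourteen arm-by-visit cells, T0 included.** C(14,2) = 91 pairs, of which 7 compare the arms at the same visit. With 14 × 15 − 14 = 196 error df, the Tukey critical value on the t scale is 3.40, against 2.05 for a single-visit t-test.

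**The case against.** The strongest reply is that the sentence speaks of groups, and Selection Criteria defines the groups as the two techniques. Taken literally, the arms are compared at each time point, and step 1 shows that this test is valid. The document never says that visits will be pooled or used as levels. This reply stands. A reader might infer that the planned analysis will produce false positives at 22–37%, or that its standard errors are wrong in both directions. The text does not support that: steps 3 to 5 describe what would happen under readings that the plan leaves open.

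A reader might also infer that a difference between techniques in how oedema resolves cannot be tested with the stated method. That is not so. A change score per patient, such as T6 minus T1, could be compared between arms with the same test, and a two-group test of one score per patient keeps its level. Superimposing scans, described under Processing of 3D Images, may already yield a within-patient change. What is missing is any statement that such an analysis will be done.

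The reply does not rescue the plan. The literal reading makes Tukey redundant and leaves six postoperative tests with no primary visit or multiplicity rule. It also gives no role to the preoperative values, although the aim concerns change.

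**Conclusion.** The method sentence does not match the design and should be replaced before analysis. That Tukey is redundant for two arms, and that no repeated-measures, change or group-by-visit analysis is specified, follows from the document without assumptions.

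On the literal reading the cost is multiplicity: a 17–24% chance of at least one false positive over six postoperative visits. The pooled-visit error rates, the inflated standard errors for visit contrasts and the 91-pair Tukey threshold are conditional on uses that the plan does not state. All these figures rest on the assumed alpha and on an equal correlation of 0.3 to 0.7. The conflict between 15 and 25 per arm is a separate matter; it hardly moves the type I error figures and does not alter the conclusion.

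**What to change.** Delete Tukey and replace the sentence with wording such as:

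> Oedema volume change from T0 at T1–T6 will be analysed with a linear mixed model (SPSS MIXED) with group, visit and group × visit as fixed effects and within-patient correlation (unstructured, or compound symmetry if it does not converge). One visit is pre-specified as primary. Group differences with 95% CI at the other visits are secondary, with a stated multiplicity adjustment, or are labelled exploratory. Each of the seven soft-tissue measurements (at one pre-specified postoperative visit) and ROE (at 6 months) will be compared between groups by ANCOVA adjusting for its preoperative value.

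The sponsor must name the primary oedema visit and the soft-tissue visit. Repeated-measures ANOVA would be an acceptable alternative for oedema. The cost is SAP wording and slightly more analysis work; no new data or software are needed.
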